### 10.4 Study Drug Information and Dosage

## 10.4.1 Identification and Description of Investigational Drug

Opaganib is supplied as Capsules 250 mg, containing 250 mg opaganib along with excipients in white opaque hard gelatin capsules.

Opaganib will be supplied in bottles, each bottle containing 28 capsules

Placebo will be supplied in bottles, each bottle containing 28 capsules

For the treatment phase of the study, treatments will be blinded.

#### 10.4.2 Packaging and Labeling

The study medication will be packaged in bottles and labelled by the Sponsor.

The labels will include:

Name and contact information for the Sponsor

Route of administration: oral or nasogastric tube

Quantity supplied: 28 per bottle

Pharmaceutical dosage form: Capsules 250 mg

Storage conditions: store drug at room temperature 15-30°C (59-86°F)

CAUTION: New Drug – Limited by Federal Law To Investigational Use

Lot number

Manufacturing date in day/month/year format.

#### 10.4.3 Storage and Handling of Investigational Drug

Study drug should be stored at room temperature 15-30°C (59-86°F)

## 10.5 Study Drug Administration

Study drug will be administered with food (after a light to moderate meal) and followed by 240 mL (8 fluid ounces) of water. If the patient can only take opaganib through a nasogastric tube, the contents of the capsule will be suspended in 20 cc normal saline solution and pushed through the nasogastric tube and flushed adequately with sterile water. If the patient is being tube-fed, study drug should be administered shortly after (approximately 15-30 minutes) a tube feeding.

#### 10.5.1 Study Drug Dose Modification Plan for Study Drug Suspected Toxicities

Patients may undergo step-wise dose reduction to one capsule Q12 hours, as shown below. Patients who develop study drug related toxicity of  $\geq$  Grade 2 at one capsule Q12 hours will not be permitted further dose reduction, and treatment will be discontinued. These patients will then enter a 2-week off-study drug safety follow-up period

NCI CTC 5.0 Criteria	Study Drug Modification Instructions
Any Grade 1 toxicity	For all Grade 1 toxicities, the Investigator may continue with study drug per the Investigator's discretion, without discussion with the sponsor
Any ≥ Grade 2 toxicity	The physician should discuss with the sponsor opaganib-related Grade 2 or greater toxicities that are likely to result in study drug discontinuation. A dose reduction may be considered as an alternative for continued treatment, after consultation with and approval by the sponsor. The physician should discuss with the sponsor opaganib-related Grade 2 or greater toxicities that are likely to result in study drug discontinuation. Please see criteria for stopping study drug in section 10.5.2).
Any ≥ Grade 2 toxicity (specifically neuropsychiatric)	The physician should discuss with the sponsor opaganib-related Grade 2 or greater toxicities that are likely to result in study drug discontinuation. Please see criteria for stopping study drug in section 10.5.2).

Dose Level	Dose (mg AM/PM)
1 (planned)	2 capsules/2 capsules
-1	1capsule/1 capsules

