#### 10 STUDY DESIGN

## **10.1 Overall Investigation Plan**

This is a phase 2a, proof of concept, multi-center randomized double-blind, parallel arm, placebo controlled study. The study is planned be performed in the US and in other countries, in approximately 15 clinical sites.

After informed consent is obtained, patients will enter a screening phase for no more than 3 days, to determine eligibility. Approximately 40 eligible patients will be randomized to receive either opaganib added to standard of care, or matching placebo added to standard of care, in a randomization ratio of 1:1. Treatment assignments will remain blinded to the patient, investigator and hospital staff, as well as the sponsor. As there is currently no consensus for a definitive treatment specifically targeting the SARS-CoV-2 virus causing COVID-19 (K. Wilson, 2020), standard of care will refer to regional, institutional or physician directed therapies, that may be implemented during the COVID-19 pandemic.

Study participants will receive either opaganib 2 x 250 mg capsules (500 mg) every 12 hours, or matching placebo, in addition to standard of care (pharmacological and/or supportive). Study drug will be administered every day for 14 days (Day 1 to Day 14), unless the patient has been discharged from the hospital without requiring supplemental oxygen, in which case study drug will only be administered to Day 10.

All participants will be followed up for 4 weeks after their last dose of study drug, which may occur at the end of the 2-week double-blind treatment phase or after premature study drug discontinuation, based upon patient or physician determination.

The maximum duration of study participation will be 45 days (including up to 3 days screening; 2 weeks double-blind (DB) phase and 4-weeks off-study drug follow-up).

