#### 12.1.5 Safety Follow-up (28 days after last dose of study drug)

- Concomitant medications
- Adverse Events
- Physical exam
- Vital signs (temperature, blood pressure, pulse rate, respiratory rate and oxygen saturation by pulse oximeter)
- Oxygen requirement (L/min)

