#### 13.2 Secondary

- 1) Time to 50% reduction from baseline in supplemental oxygen based on oxygen flow in L/min
- 2) The percentage of patients no longer receiving supplemental oxygen for at least 24 hours by Day 14
- 3) The time to two consecutive negative swabs for SARS-CoV-2 by PCR, at least 24 hours apart
- 4) The percentage of patients with at least two consecutive negative swabs, followed by continued negative swabs, for SARS-CoV-2 by PCR at Day 14
- 5) The percentage of patients requiring intubation and mechanical ventilation by the end of the 2-week off-study-drug follow-up
- 6) The time to intubation and mechanical ventilation
- 7) The percentage of patients with at least one measurement of fever at baseline (defined as temperature >38.0 C[100.4 F]), who are afebrile (defined as temperature <37.2C [99 F]) at Day 14
- 8) Mortality due to any cause at Day 30

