### 15.5 Other Safety Considerations

Patients will be followed for at least 28 days after discontinuation of study medication. When possible, the patient will come to the clinic for an in-person assessment. If not possible for logistic reasons, the assessment may be performed by phone with a study coordinator.

All AEs must be recorded and followed until resolution or for at least 28 days after discontinuation of study medication, whichever comes first.

Any clinically significant changes noted during interim or final physical examinations, electrocardiograms, x-rays, and any other potential safety assessments, whether or not these procedures are required by the protocol, should also be recorded on the AE page of the eCRF.

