### 15.5.1 Serious Adverse Events

A written report of all SAEs that occur after the administration of study drug and during the study (ending with the safety follow-up visit, 2 weeks off-study drug) must be submitted to the IRB/ethics committee (EC) and the sponsor. SAEs/SUSARs must be reported to the Sponsor within 24 hours for a determination of expedited reporting to FDA. In all SAE reports, the investigator will advise whether or not the SAE is judged to be related to study drug administration. All SAEs that are judged by the investigator to be at least possibly related to study drug administration must be reported to the sponsor regardless of how much time has elapsed since the last exposure to study drug. All SAEs must be submitted to the IRB/EC in an annual report per local reporting guidelines.

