This time to event endpoint will be calculated as the number of days from baseline (Day 1) of study medication until the first occurrence of two consecutive negative swabs for SARS-CoV-2 by PCR, at least 24 hours apart (the event of interest). Patients who early terminate the study before reaching this event will have their time censored at the last valid observation time point. Patients who will die within the follow-up timeframe will be censored at the time of the end of the follow-up period, thus taking the highly unfavorable possible outcome for this endpoint. The time frame for this endpoint is from Day 1 until end of off-study-drug follow-up. Additional analysis will be performed in the time frame of the 14-day-treatment DB Phase period (sensitivity analysis).

4. The time to two consecutive negative swabs for SARS-CoV-2 by PCR, at least 24 hours apart, followed by continued negative swabs

This time to event endpoint will be defined similarly to the 3rd secondary efficacy endpoint, where the event of interest is the first occurrence of two consecutive negative swabs for SARS-CoV-2 by PCR, at least 24 hours apart, followed by continued negative swabs. The time frame for this endpoint is from Day 1 until end of off-study-drug follow-up.

Additional analysis will be performed in the time frame of the 14-day-treatment DB Phase period (sensitivity analysis).

5. The percentage of patients requiring intubation and mechanical ventilation

The percentage of patients requiring intubation and mechanical ventilation by **Day 30** will will be defined per subject as a binary ("Failure" / "Success") variable with "Failure" indicating that a subject had a reported requirement of intubation and mechanical ventilation any time before 30-days following first study dose, and "Success" otherwise. Death during this time frame will be regarded as "Failure" as well.

The percentage of patients requiring intubation and mechanical ventilation by **Day 14** will also be estimated in a similar way. Death before day 14 will be regarded as "Failure" as well.

6. The time to intubation and mechanical ventilation.

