14.2.6	Percentage of patients requiring intubation and mechanical ventilation by the end of the 4-week off-study-drug follow-up	mITT
14.2.7.1-2	Time to intubation and mechanical ventilation         (two time frames: up to end of follow up; up to Day 14)	mITT
14.2.8	The percentage of patients with at least one measurement of fever at baseline, who are afebrile at Day 14	mITT (with Fever at baseline)
14.2.9	The percentage of patients who are afebrile at Day 14	mITT
14.2.10	Mortality due to any cause at Day 30	mITT
Explor	atory Efficacy endpoints	
14.2.11.1	Summary of Systemic Markers of Inflammation and Change from Baseline by Visit and Treatment Groups	mITT
14.2.11.2	Systemic Markers of Inflammation Normal/Abnormal and Clinically Interpretations Results by Visit and at Any Post Baseline Time Point and by treatment Group	mITT
14.2.11.3	Shift from baseline to each Visit and 'Any Time Post Baseline' of Systemic Markers of Inflammation Abnormal Values by Treatment Group	mITT
14.2.11.4	Shift from baseline to each Visit and 'Any Time Post Baseline' of Systemic Markers of Inflammation Clinically Interpreted Test Results by Treatment Group	mITT
Exposu	ire and Safety	
14.3.1.1	Study Drug Exposure by Treatment Group	Safety
14.3.1.2	Treatment Compliance by Treatment Group	Safety
14.3.2.1	Summary of Treatment Emergent Adverse Events by Treatment Group	Safety
14.3.2.2	TEAEs by SoC and PT by Treatment Group	Safety
14.3.2.3	TE-SAE by SoC and PT by Treatment Group	Safety
14.3.2.4	Grade 3 or Above TEAE by SoC and PT by Treatment Group	Safety
14.3.2.5	Grade 3 or above TESAE by SoC and PT by Treatment Group	Safety
14.3.2.6	Treatment related TEAE by SoC and PT by Treatment Group	Safety
14.3.2.7	Treatment related TESAE by SoC and PT by Treatment Group	Safety
14.3.2.8	TEAE resulting in dose reduced by SoC and PT by Treatment Group	Safety
14.3.2.9	TEAE resulting in drug withdrawn by SoC and PT by Treatment Group	Safety

Summary number	Title	Population
14.3.2.10	Any TEAE with an outcome of death by SoC and PT by Treatment Group	Safety
14.3.2.11	TEAEs by SOC, PT and Maximum severity by Treatment Group	Safety
14.3.2.12	TEAEs by SOC and PT by maximal Relationship to Treatment by Treatment Group	Safety
14.3.2.13	TEAEs of Special Interest by Treatment Group	Safety
14.3.3.1.1	Chemistry Results and Change from Baseline by Visit and by Treatment Group	Safety

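### Protocol 10.5.1 and 15.5.1 state a 2-week off-drug follow-up that contradicts the 4-week follow-up set for all participants

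*Protocol*

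**What the plan says.** **The general rule.** Protocol 10.1 states: "All participants will be followed up for 4 weeks after their last dose of study drug". The same sentence names premature discontinuation as one way the last dose may come about. The synopsis and SAP 3.1 repeat the rule. The heading of Protocol 12.1.5 begins "Safety Follow-up (28 days after last dose of study drug". Protocol 15.5 adds: "Patients will be followed for at least 28 days after discontinuation of study medication". Protocol 10.1 gives a maximum participation of 45 days.

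**The two departures.** Protocol 10.5.1 deals with patients who have already been reduced to one capsule every 12 hours and then have related toxicity of Grade 2 or higher. Treatment stops, and "These patients will then enter a 2-week off-study drug safety follow-up period". Protocol 15.5.1 requires a written report to the IRB/EC and the sponsor of SAEs that occur after dosing and during the study, "ending with the safety follow-up visit, 2 weeks off-study drug".

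**A related endpoint.** Protocol 13.2, item 5 (and the synopsis) reads: "The percentage of patients requiring intubation and mechanical ventilation by the end of the 2-week off-study-drug follow-up". SAP 3.2.2 counts the same event "any time before 30-days following first study dose". The title of table 14.2.6 in SAP 12 is "Percentage of patients requiring intubation and mechanical ventilation by the end of the 4-week off-study-drug follow-up".

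**The concern.** Sections 10.5.1 and 15.5.1 are operating instructions. A site turns to 10.5.1 when it stops a patient for toxicity, and to 15.5.1 when it decides whether an SAE needs a written report. Each gives half the interval stated elsewhere, and neither gives a reason or is marked as an exception.

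The patients under 10.5.1 have had drug-related toxicity even at the reduced dose, so late safety information on them is particularly useful. SAP 8.3 sets no end date for treatment-emergent events. An event starting on off-drug days 15 to 28 would therefore count, but a site that closed follow-up at 2 weeks would not see it. In the Schedule of Assessments, the safety follow-up is also the only scheduled contact after Day 14. If it moves to 2 weeks off drug, no scheduled contact covers Day 30 for these patients.

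**Working it through.** **Step 1: reproduce the plan's figure.** Protocol 10.1 gives up to 3 days of screening, 2 weeks of treatment and 4 weeks of follow-up.

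- With 4 weeks: 3 + 14 + 28 = 45 days, as stated.
- With 2 weeks: 3 + 14 + 14 = 31 days, which is 14 days short.

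**Step 2: when follow-up ends.** Let the last dose fall on Day d, with d no later than 14. The 2-week rule ends on Day d + 14 and the 4-week rule on Day d + 28. The shortfall to Day 30 under the 2-week rule is 30 − (d + 14) = 16 − d. The values of d are examples; the documents do not say when such stops would occur.

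| Last dose (d) | 2-week rule ends | 4-week rule ends | 2-week rule short of Day 30 by |
|---|---|---|---|
| 3 | Day 17 | Day 31 | 13 days |
| 7 | Day 21 | Day 35 | 9 days |
| 14 | Day 28 | Day 42 | 2 days |

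Since 16 − d is positive for every d up to 14, the 2-week rule never reaches Day 30. The 4-week rule reaches it for any d of 2 or more. With d = 1 it would end on Day 29, but a patient stopped under this part of 10.5.1 has first been reduced to one capsule, so d = 1 is hardly possible. The off-drug time left unobserved is 28 − 14 = 14 days, or 14/28 = 50%.

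**Step 3: effect on the Day 30 endpoints.** SAP 3.2.2 counts a patient as a mortality success only if known to be alive at Day 30. For time to intubation, it censors patients who leave the study alive and without the event at their last valid observation. SAP 7.3 handles loss to follow-up in the mortality and intubation percentages by Kaplan-Meier estimation with the same censoring. The analysis is therefore specified, but information between Day d + 14 and Day 30 is lost. With about 20 patients per arm, one such patient is 1/20 = 5% of an arm.

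**Step 4: the SAE window.** Set side by side:

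- 15.5.1 closes the written-report window at a visit 2 weeks off drug. Section 12.1.5 puts that visit at 28 days.
- 15.5.1 itself keeps SAEs judged at least possibly related reportable to the sponsor without a time limit.
- Sections 14 and 15.3 require SAEs to be reported to the sponsor within 24 hours and set no end date. Section 15.3 includes deaths whatever their cause.
- Section 15.5 keeps patients under follow-up, and their AEs recorded, for 28 days.

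What 15.5.1 leaves outside its own window is SAEs on off-drug days 15 to 28 judged less than possibly related. The sponsor should still receive these under Sections 14 and 15.3. The gap is mainly in the written report to the IRB/EC, and 15.5.1 also requires an annual submission of all SAEs to that body.

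**The case against.** The strongest reply is that the general rule is stated repeatedly and expressly covers early stops. A site that follows patients for 28 days complies with 10.1, 12.1.5 and 15.5 and breaches nothing in 10.5.1, which says what period patients enter and not that participation ends there. Section 10.3 also has patients stopped for AEs monitored until resolution or stability. On this view, lost Day 30 data are remote. Much of this stands: a careful site would probably use 4 weeks, and harm arises only from a literal reading. It does not remove the contradiction, because the more specific instruction carries the shorter interval. SAP 3.1 repeats the 4-week rule, but the SAP has no provision for 10.5.1 patients and no SAE reporting window, so its precedence over the protocol does not settle either passage.

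Three stronger readings are tempting, and the documents do not support them.

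- *Late unrelated SAEs go unreported.* Sections 14, 15.3 and 15.5 still require them to be recorded and reported to the sponsor.
- *The intubation endpoint has no settled time point.* With d = 14, the protocol wording closes on Day 28, SAP 3.2.2 on Day 30 and the table title on Day 42. But the SAP preface gives the SAP precedence, SAP 3.2.2 sets Day 30, and SAP 10 records that choice. The table list in SAP 12 is described there as the one foreseen at study onset, with the final list kept in study files.
- *The 2-week text is a remnant of a scheme with longer dosing.* Section 7.4 mentions dosing for up to 4 weeks, and 12.1.4 mentions Day 28 as an end of treatment, which fits that idea. No protocol change log is provided, so it remains a guess.

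**Conclusion.** The inconsistency is real and should be corrected, at low severity. The protocol gives no sign that either 2-week statement is an intended exception to a rule that covers all participants.

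In size, a literal reading of 10.5.1 costs each affected patient 14 of 28 off-drug days and stops 2 to 13 days before Day 30 in the examples shown. This rests on a site taking the 2-week period as the end of observation. The number of such patients is not given and is probably small. The 15.5.1 error bears on reporting for all of the approximately 40 patients, but its practical effect is largely confined to the IRB/EC report of SAEs judged less than possibly related. The primary endpoint, which closes at Day 14, is unaffected, as is the sample size.

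**What to change.** Two phrases need to change.

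- **Protocol 10.5.1:** replace the 2-week safety follow-up with a 4-week off-study-drug follow-up, and refer to Section 12.1.5.
- **Protocol 15.5.1:** date the safety follow-up visit at 28 days off study drug instead of 2 weeks.

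As clerical alignment only, the synopsis and Protocol 13.2 (item 5) and the title of SAP table 14.2.6 could be set to Day 30 from first dose, which SAP 3.2.2 already uses. Section 15.5 needs no change.

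Sites already working to 4 weeks have nothing to add. A site that had used 2 weeks would add at most one 28-day contact for each patient stopped under 10.5.1, which Section 15.5 allows by phone. It would also send the IRB/EC a written report of any SAE on off-drug days 15 to 28; the report to the sponsor is already required.

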#### 10.3 Patient Discontinuation Criteria

A patient may be withdrawn from the study treatment or the study for any of the following reasons:

- Request of the patient or patient's representative
- The patient has experienced an AE that meets protocol defined stopping criteria (refer to Section 10.5.2)
- AEs or adverse device effects (ADEs) based on the judgment of the InvestigatorThe Investigator decides that it is in the patient's best interest
- The patient is noncompliant with the protocol

- Lost to follow-up
- Death

If a subject is withdrawn at any time, the reason(s) will be recorded in the relevant section of the eCRF. Patients who discontinue from study treatment and remain in the study, will continued to be monitored per the Schedule of Assessments until Day 14.

Patients discontinued due to AEs or ADEs will be monitored until resolution or stability of the event based on the judgment of the investigator.

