## 10.5.2 Criteria for Stopping Study Drug

At any time during the study, participants will stop of study drug if it is determined that they have experienced any of the following adverse events (refer to section 15.2 Table 3 for Adverse Event Grade Definitions):

- Any neuropsychiatric adverse event of Grade 3 severity
- Hallucinations of any severity (any Grade)
- Nausea of Grade 3 severity
- Vomiting of Grade 3 severity

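### For a suspected drug-related Grade 1 hallucination, protocol 10.5.1 permits study drug to continue while 10.5.2 requires it to stop, and no text says which governs

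*Protocol*

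**What the plan says.** Protocol section 10.5.1 covers toxicities suspected to be due to study drug. It opens with a general permission: "Patients may undergo step-wise dose reduction to one capsule Q12 hours, as shown below". A table then gives instructions by grade.

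- **Grade 1 row:** "For all Grade 1 toxicities, the Investigator may continue with study drug per the Investigator's discretion, without discussion with the sponsor". It has no exception and no reference to another section.
- **General row for Grade 2 or higher:** the physician discusses with the sponsor related events likely to lead to discontinuation. It adds: "A dose reduction may be considered as an alternative for continued treatment, after consultation with and approval by the sponsor". It then refers to 10.5.2.
- **Neuropsychiatric row**, headed "Any ≥ Grade 2 toxicity (specifically neuropsychiatric"): the same discussion with the sponsor and the same reference to 10.5.2, but no sentence on dose reduction.

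Section 10.5.2 follows directly. It states that "participants will stop of study drug if it is determined that they have experienced any of the following adverse events". The list includes "Any neuropsychiatric adverse event of Grade 3 severity" and "Hallucinations of any severity (any Grade"). It has no condition on relatedness to study drug.

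**The concern.** A site that works from the table finds a rule for every Grade 1 toxicity and no signal that one kind of Grade 1 event is treated differently a few lines later. The row also removes the discussion with the sponsor in which a misreading might be noticed before the next dose. A patient whom one section takes off study drug could thus stay on it under the other.

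The event is not remote. Section 6.4.1.2 names hallucinations among the neuropsychiatric effects seen in the myeloma study, and SAP section 8.3.1 adds neuropsychiatric events to the events of special interest. With about 15 sites and about 40 patients, most sites would contribute only a few patients each, so a difference in reading between sites would be hard to see in the data.

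Several planned summaries depend on the action taken: premature treatment discontinuation (SAP 6.2), dose reductions (SAP 8.2.1), and treatment-emergent events leading to dose reduction or drug withdrawal (SAP 8.3). The safety board also reviews dose reductions (protocol 15.5.4).

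**Working it through.** The plan gives no figure to reproduce. The check is to take each kind of event, apply 10.5.1 and 10.5.2 to it, and see whether one instruction results. The event is assumed to be suspected drug-related and to occur at the planned dose, because 10.5.1 already requires discontinuation for a related event of Grade 2 or higher at the reduced dose.

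| Event | 10.5.1 | 10.5.2 | Result |
|---|---|---|---|
| Grade 1 hallucination | Grade 1 row: may continue, no sponsor discussion, no reference to 10.5.2 | Stop (any grade) | Conflict |
| Grade 2 hallucination | Both Grade 2-or-higher rows fit; both refer to 10.5.2 | Stop (any grade) | Settled by the reference |
| Grade 2 neuropsychiatric event, not hallucination | Both rows fit; one offers dose reduction, one is silent | Not listed (Grade 3 only) | Not settled |
| Grade 3 neuropsychiatric event | Both rows fit; both refer to 10.5.2 | Stop | Settled by the reference |

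**Row 1.** The Grade 1 text is a permission and 10.5.2 is a mandate. An investigator who stops the drug breaches neither section. One who continues acts within 10.5.1 and breaches 10.5.2. The conflict lies in that second case.

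**Row 3.** The difference arises by omission. The neuropsychiatric row does not bar dose reduction, and the opening sentence of 10.5.1 allows it with no neuropsychiatric exception. Yet the row differs from the general one essentially by leaving that option out, so a reader may suppose that a different rule was meant.

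**Search for a tie-breaker.** No text ranks one protocol section, or one table row, over another. The only precedence rule found, in the SAP preface, ranks the SAP over the protocol, and the SAP sets no rule for stopping or reducing dose.

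**Which outputs are touched.** The Grade 1 conflict is between continuing and stopping, so it can move discontinuation and events leading to withdrawal, but not dose-reduction counts. The Grade 2 gap can move dose-reduction counts as well.

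**Scale.** Section 17.1 plans 20 patients per arm, so one patient is 1/20 = 5 percentage points of an arm's discontinuation rate. This is the weight of one patient, not an estimate of how many are affected.

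**The case against.** The best defence is that a specific mandatory rule placed directly after a general permission governs it, and that most investigators would read the two sections that way. If they do, the defect is a missing cross-reference. That is a fair account of the likely intention. It does not remove the problem: the row covers every Grade 1 toxicity without exception, the other two rows carry the reference and this one does not, and nothing states the order of precedence.

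On the Grade 2 gap, dose reduction needs sponsor approval, and both rows send events likely to end in discontinuation to the sponsor. That central check limits variation between sites, which is why this point is secondary.

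Three stronger readings are tempting, and the documents do not support them.

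- *Sites may continue without the sponsor knowing.* The row waives discussion, not reporting. Section 14 still requires all adverse events to be reported to the sponsor, and the safety board reviews all adverse events.
- *Section 10.3 turns the mandatory stop into an option.* Its wording, "A patient may be withdrawn from the study treatment or the study for any of the following reasons", introduces a general list that also includes loss to follow-up and death. The relevant item calls the criteria protocol-defined and points to 10.5.2. It does not restate the stopping rule.
- *Most treated patients would meet the conflict*, since neuropsychiatric effects occurred in 14 of 21 (67%) and 8 of 13 (62%) patients in the earlier studies. Those counts cover effects such as insomnia, anxiety and dizziness and include doses above the planned one. In the myeloma study all affected patients were also taking narcotic analgesics. Neither study gives a count of Grade 1 hallucinations or of Grade 2 events.

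**Conclusion.** The point holds for one case in full: a suspected drug-related Grade 1 hallucination has a permission to continue in 10.5.1 and a mandatory stop in 10.5.2, with no stated precedence. A hallucination judged unrelated falls outside 10.5.1 and raises no conflict. The Grade 2 overlap is a lesser ambiguity, limited to neuropsychiatric events other than hallucinations.

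Sites may, not will, handle such events differently. The consequence is for patient safety and for the interpretation of the safety summaries. Its frequency cannot be estimated from the documents.

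A reader might infer that the primary result is also at risk. That is not shown: protocol 17.3 plans to collect oxygen data to Day 14 after treatment is stopped, and the primary analysis keeps every randomized patient who received a dose. The conclusion rests on the wording alone and on no assumption about effect size, variance or event rate.

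**What to change.** The sponsor should reconcile 10.5.1 and 10.5.2 on two matters.

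1. Give a Grade 1 hallucination one instruction and state it consistently in both sections.
2. Make clear in the table which row applies to a Grade 2 neuropsychiatric event, and whether dose reduction is available for it.

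The choice of clinical rule in each case belongs to the sponsor; this review takes no position on it.

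The cost is a wording change in one table and one short list, ethics review of the modification as section 16.2.6 requires, and a letter to sites. No procedure, data item or analysis is added. If patients have already been treated under the present wording, the study report can list any Grade 1 hallucination and any Grade 2 neuropsychiatric event with the action taken, using the adverse event records and the missed or reduced dose log described in SAP 8.2.2. That would show whether the ambiguity affected any patient.
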